9.4.3 Dopamine transporters scan assessment

DAT scans will be performed only in countries where it is approved.

Women of childbearing potential must have a urine (or serum if required by the site) pregnancy test prior to injection of DAT scan. The result must be confirmed as negative prior to proceeding with the injection.

Before the DAT scan injection, patients will be pretreated with stable iodine (10 drops of a saturated solution of potassium iodide) to reduce the uptake of DAT scan by the thyroid, according to the local regulation.

Patients will be injected with 3 to 5 mCi of DAT. Within a 4-hour (± 30 minutes) window following the injection, patients will undergo standard brain single-photon emission computerized tomography imaging as per the Society of Nuclear Medicine Practice Guidelines.

A central reading center will be used to read the imaging from the patients to ensure consistency and accuracy between sites.

In Part 1, patients will undergo a DAT scan within 7 days prior to randomization (Day -7 to Day -1) or on the day of randomization (Day 1, pre-dose) (See [Section 1.3.1](#)).

In Part 2, patients will undergo a DAT scan at screening (within 7 days prior to randomization [Day -7 to Day -1] or on the day of randomization [Day 1, pre-dose]) and Weeks 52, 104, 156, and 208 (See [Section 1.3.2](#) and [Section 1.3.3](#)).

9.4.4 Levodopa or other Parkinson's disease therapy

9.4.4.1 Time to initiation/intensification of levodopa/PD therapy

It is anticipated that GBA-PD patients, if entering the study on a PD medication, will be able to remain on a stable dose of the PD medications for the entire duration of the study. However, it may be considered necessary in the medical judgment of Investigator to initiate or intensify PD medications. In such occurrence, this could apply only to an immediate release levodopa formulation. If PD medications are to be initiated or intensified, patients will be asked to return for an additional study visit on site. This also holds true if a patient requires a change in his/her PD medication. The Investigator will document any new medications or changes in medication at each study visit on the Concomitant Medication Log.

In Part 2 only, time to initiation of levodopa or other PD therapy (for patients not on levodopa/other PD therapy at baseline) or to increased dose of levodopa/other PD therapy (for patients on levodopa/other PD therapy at baseline) will be calculated.

9.4.4.2 Reduction of levodopa/PD therapy

In Part 2 only, there might be a possibility that GBA-PD patients, if entering the study on a PD medication, would be able reduce their dose of the PD medication. If PD medications are to be reduced or stopped, the Investigator will document these changes in medication at each study visit on the Concomitant Medication Log.

9.4.5 Scales and questionnaires

9.4.5.1 Montreal cognitive assessment score

In early PD, when cognitive deficits occur, they are subtle and mild and the patients usually perform in the normal range on the widely used Mini Mental State Examination. The MoCA is a rapid screening instrument like the Mini Mental State Examination but was developed to be more sensitive to patients presenting with mild cognitive complaints. It assesses short-term and working memory, visuospatial abilities, executive function, attention, concentration, language, and orientation. The total score ranges from 0 to 30 (see [Section 17 \[Appendix I\]](#)). This assessment will be scored by an independent blinded rater.

In Part 1, the changes from baseline to Week 8 in MoCA score will be assessed, separately for Japanese and non-Japanese patients.

In Part 2, the changes in MoCA score from baseline to Week 52 and from baseline to Week 104, Week 156, and Week 208 will be assessed.

9.4.5.2 Oral symbol digit modalities test score

The SDMT assesses divided attention, visual scanning, and motor speed. After being presented with a coding key, the patient is required to pair the number with the corresponding symbol as rapidly as possible and within 90 seconds (see [Section 17 \[Appendix J\]](#)). Symbol Digit Modalities Test requires the subject to substitute a number for its corresponding geometric figure. There are 9 figures. On the record form, there are a series of rows containing geometric figures in the top half, but the bottom half is left blank. When it is clear that the subject understands the task, he or she is told to fill in the remaining boxes as quickly as possible, completing one box at a time, one row at a time, before proceeding to the next. Skipping from box to box with the same geometric figure is not permitted. Subjects receive one point for each correctly completed box. The total score is the total number of correctly completed boxes in the time allowed. The practice items are not counted in the scoring. This assessment will be scored by an independent blinded rater.

The test can be administered by having the subject write out the correct response or by having the subject report the correct answer (ie, number) aloud. Higher scores are better scores and the range of scores can be from 0 to 110 for SDMT oral scores.

Parkinson's disease patients have motor skill deficits, therefore oral SDMT will be used in this study as this version has greater sensitivity than the written version. The blinded rater will read the instructions to the patient, point to the open spaces on the form and record the answer from the patient.

In Part 1, the changes from baseline to Week 8 in SDMT oral score will be assessed, separately for Japanese and non-Japanese patients.

In Part 2, the changes in SDMT oral score from baseline to Week 52 and from baseline to Week 104, Week 156, and Week 208 will be assessed.

9.4.5.3 Trail making test A and B score

The TMTs are popular neuropsychological instruments used either alone as a screening instrument for detecting neurological disease and neuropsychological impairment or as part of a larger battery of tests. The tests are believed to measure the cognitive domains of processing speed, sequencing, mental flexibility, and visual–motor skills (see [Section 17 \[Appendix K\]](#)). It consists of two parts in which the patient is instructed to connect a set of 25 dots as quickly as possible while still maintaining accuracy. The test can provide information about visual search speed, scanning, speed of processing, mental flexibility, as well as executive functioning. It is sensitive to detecting cognitive impairment associated with dementia. This assessment will be scored by an independent blinded rater.

Scoring will include total score for each TMT-A and TMT-B as well as the change in the difference between TMT-B score minus TMT-A score.

In Part 1, the changes from baseline to Week 8 in TMT-A and TMT-B score including the change in the difference between TMT-B minus TMT-A score will be assessed, separately for Japanese and non-Japanese patients.

In Part 2, the changes from baseline to Week 52 and from baseline to Week 104, Week 156, and Week 208 in TMT-A and TMT-B score including the change in the difference between TMT-B minus TMT-A score will be assessed.

9.4.5.4 Beck depression inventory, second edition

Depression will be monitored during the study by using the BDI-II; see [Section 17 \(Appendix L\)](#). Beck Depression Inventory, second edition is a 21-question, multiple-choice, self-report inventory. It is composed of items relating to symptoms of depression such as hopelessness and irritability, cognitions such as guilt or feelings of being punished, as well as physical symptoms such as fatigue, weight loss, and disinterest in sex.

The wording of the BDI-II is clear and concise. The test contains 21 items, most of which assess depressive symptoms on a Likert scale of 0-3. The two exceptions to this are questions 16 and 18. Question 16 addresses changes in sleeping pattern, while question 18 addresses changes in appetite. Patients will be asked to report their own feelings over the past 2 weeks instead of 1 week, as in the BDI and BDI-IA. The reason for this is to be consistent with the Diagnostic and Statistical Manual of Mental Disorders, 4th Edition criteria for depression. There were also two items added to indicate any directional changes in eating and sleeping patterns. Finally, all forms of the inventory are written at the 5th grade reading level.

Clinical interpretation of scores is accomplished through criterion-referenced procedures utilizing the following interpretive ranges: total BDI-II scores of 0-13 indicate minimal depression, scores of 14-19 indicate mild depression, scores of 20-28 indicate moderate depression, and scores of 29-63 indicate severe depression. The BDI-II will be performed at every study visit in this trial.

If a patient has a score of ≥ 20 or if the patient has a score < 20 but answers “yes” to answer 2 or 3 of question 9, the patient must be referred to their health care professional for psychiatric evaluation. This will be captured as an AE. The participant may continue the study, but this is dependent on the judgment of the PI.

In Part 1, BDI-II will be administered at every study visit, except on Visits 3 and 4 (Week 0, Days 2 and 3) and Visit 7 (Week 4, Day 2).

In Part 2, the changes from baseline to Week 52 and from baseline to Week 104, Week 156, and Week 208 in BDI-II score will be assessed.

9.4.5.5 Clinical global impression scale

The CGI is a 3-item observer-rated scale that measures illness severity (CGIS), global improvement or change (CGIC), and therapeutic response (see [Section 17 \[Appendix M\]](#)). Each component of the CGI is rated separately; the instrument does not yield a global score. CGI will be scored by an independent blinded reader.

The CGIS is rated on a 7-point scale, with the severity of illness scale using a range of responses from 1 (normal) through to 7 (amongst the most severely ill patients). CGIC scores range from 1 (very much improved) through to 7 (very much worse). Treatment response ratings should take account of both therapeutic efficacy and treatment-related AEs and range from 0 (marked improvement and no side effects), and 4 (unchanged or worse and side-effects outweigh the therapeutic effects).

In Part 1, CGI scores will be assessed on Day 1 and Week 8, separately for Japanese and non-Japanese patients.

In Part 2, CGI scores will be assessed on Day 1 and Week 52.

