10 STUDY PROCEDURES

In order to ensure proper evaluation of efficacy, the staff of each study center will include the following physicians: a primary treating neurologist, a neurologist Sub-Investigator and a minimum of 2 blinded examining neurologist/raters. The primary treating neurologist, who can serve as the PI, will have overall responsibility to lead the site study team (physicians, pharmacists, technicians, nurses, and clinical coordinators) in all aspects of the study. The primary treating neurologist/PI will also have a neurologist Sub-Investigator who can back up the PI when/if needed. The blinded examining neurologist/raters must be experienced neurologists, or qualified non-physician health professionals who meet a predetermined level of experience in evaluating GBA-PD patients including examining GBA-PD patients and scoring the various scales when permitted by local laws, health authority rules, and ethics committee requirements. This delineation assures that AEs or other health issues for any patient do not influence the neurological assessment. Both the treating neurologist and blinded examining neurologist/ rater must have a minimum of 2 years of PD clinical experience.

Treating neurologist

The treating neurologist will be responsible for evaluation of patient eligibility; supervision of IMP administration; assessing and treating of AEs; assessing, confirming, and managing any GBA-PD issues; and monitoring of safety assessments, including routine laboratory results and concomitant medications. As much as possible, the same treating neurologist, be it the PI or Sub-Investigator, must maintain that role for a given patient throughout the study.

Examining neurologist/blinded rater

Every effort should be made to maintain the same blinded raters throughout the study. In case the rater must change, new blinded raters must be trained and remain throughout the duration of the study. For a given patient, one blinded rater does not have to perform all the assessments. However, each questionnaire (MDS-UPDRS [including H&Y], PD-CRS, MoCA, SDMT [oral], TMT-A, TMT-B, and CGI) should be scored by the same blinded rater throughout the study. Of note, only MDS-UPDRS and PD-CRS require a certified blinded rater.

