The examining neurologist/blinded rater will be responsible for conducting all the efficacy assessments and for determining the scores, and must be certified for MDS-UPDRS and PD-CRS rating prior to any involvement in the study. Throughout the study, the examining neurologist/rater must not be involved with any other aspect of patient care and management and must remain blinded to the patient's treatment and safety profile (AEs, concomitant medications and laboratory results). Moreover, he/she must also not read the protocol, ensuring accurate rater-blinded assessments. This person should instead refer to the schedule of assessments.

All other investigational site staff must refrain from discussing any aspects of the protocol and/or safety issues with the examining neurologist. The examining neurologist/blinded rater should maintain the role for a given patient throughout the study. The study site is responsible for appointing a backup examining neurologist/rater in the case the primary is unable to fulfill the

role and that person is responsible for conducting the remainder of the assessments for the patient throughout the remainder of the study. The role of the treating neurologist and the examining neurologist is NOT interchangeable throughout the study even for different patients.

The Clinical Coordinator may be a nurse or physician who will be responsible for coordinating and assisting all study site staff, including patient scheduling and completion and monitoring of all patients' case report forms. He/she will be responsible for coordinating IMP administration, and collect, process, and send all blood and other forms of biological samples and requests to the central laboratory. Additionally, he/she will be responsible for administering the patient-reported questionnaires, and coordinating the conduct of the baseline MRI (without contrast).

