10.1.2.9 Visit 9: Week 52 (±14 days)

Visit 9 will be the last study visit of the blinded treatment period in Part 2.

Before dosing, the following assessments will be performed as listed in the study flow chart, [Section 1.3.2](#), which must be done in the following order:

- Whenever possible, the following scales and questionnaires should be done prior to clinical interaction with the Investigator:
 - BDI-II ([Appendix L](#))
 - PGIC ([Appendix N](#))
 - CGI ([Appendix M](#))
 - PDQ-39 ([Appendix O](#))
 - EQ-5D ([Appendix P](#))

- HRPQ ([Appendix R](#))
- FES ([Appendix Q](#))
- MDS-UPDRS, including H&Y ([Appendix F](#))
- PD-CRS ([Appendix G](#))
- Other questionnaires and scales
 - MoCA ([Appendix I](#))
 - Oral SDMT ([Appendix J](#))
 - TMT-A; TMT-B ([Appendix K](#))
- Review concomitant medications
- Physical examination
- General neurological examination
- Record of body weight measurement
- Vital signs (orthostatic): systolic and diastolic blood pressure (mm Hg), heart rate (bpm), respiratory rate (breaths/minute), and temperature (°C)
- 12-lead ECG
- Laboratory assessments (to be performed by the central laboratory):
 - Hematology: CBC, with differential and platelet count; coagulation profile: PT, PTT, and INR
 - Biochemistry: Sodium, potassium, chloride, calcium, ALT, AST, GGT, ALP, total and conjugated bilirubin, urea, serum creatinine, glucose, albumin, total proteins
- Urinalysis (dipstick) including glucose, protein, bilirubin, urobilinogen, pH, specific gravity, blood, ketones, nitrite, and leucocytes. Central urinalysis will be performed if any abnormality is observed in the urinalysis dipstick test.
- Urine pregnancy test (for WOCBP)
- Review of current medical conditions, with AE/SAE reporting (if any)
- Blood sampling for biomarker analyses, GCase activity and PK (as listed in study flow chart [Section 1.4.2](#))
- Pharmacogenetics DNA sample (optional; not applicable in Israel [[Appendix T](#)])
- Evaluate patients for eligibility (inclusion/exclusion criteria as listed in [Section 7.1](#), [Section 7.2](#), and [Section 10.1.2.10](#)) to transition to LTFU and receive GZ/SAR402671 treatment
- Full ophthalmology examination and photography (must be performed after the neurological examination)
- DAT scan

- Lumbar puncture for collection of CSF for PK (as listed in study flow chart [Section 1.4.2](#)) and biomarker analyses

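### The CGI treatment-response item asks a rater who must stay blinded to adverse events to weigh adverse events, and at Week 52 the CGI is placed ahead of the MDS-UPDRS

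*Protocol*

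**What the plan says.** Section 9.4.5.5 describes the CGI as three separately scored observer ratings: severity, change and treatment response. On the third it says: "Treatment response ratings should take account of both therapeutic efficacy and treatment-related AEs". That item runs from 0 (marked improvement, no side effects) to 4 (no benefit, and side effects outweigh the effect). The scorer is blinded: "CGI will be scored by an independent blinded reader". On timing: "In Part 2, CGI scores will be assessed on Day 1 and Week 52".

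Section 10 separates the treating neurologist, who assesses AEs, from the examining neurologist or blinded rater, and gives the reason: "This delineation assures that AEs or other health issues for any patient do not influence the neurological assessment". It lists the CGI among the blinded rater's scales: "TMT-A, TMT-B, and CGI) should be scored by the same blinded rater throughout the study". That sentence asks for the same rater over time within each scale. It does not say that one person scores all scales. The rater "must remain blinded to the patient's treatment and safety profile (AEs, concomitant medications and laboratory results"), and other site staff may not discuss safety issues with that person.

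At Visit 9 (Section 10.1.2.9) the assessments are listed as a sequence "which must be done in the following order". The CGI is in the first block, and the MDS-UPDRS and PD-CRS come after it.

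**The concern.** The treatment-response item is defined on two inputs, benefit and side effects. The person assigned to score it is barred from knowing the second. One of two things must give: the content of the item or the AE blinding of the rater.

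If the item gives way, the loss is confined to one exploratory subscore. If the blinding gives way, the consequence can reach the primary endpoint. The primary endpoint is the change in MDS-UPDRS Part II+III from baseline to Week 52, and Part III is scored by the blinded rater. The protocol separates the two roles so that AE knowledge stays away from that rating. In Part 2 the only post-treatment CGI is at Week 52, the visit of the primary contrast, and there it is sequenced before the MDS-UPDRS.

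**Working it through.** The core of this point is a comparison of text.

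**1. Can both instructions be followed?**
- Section 9.4.5.5: the CGI scorer is blinded and is to weigh treatment-related AEs.
- Section 10: the blinded rater scores the CGI and must not know the AEs.
- Using separate raters for the CGI and the MDS-UPDRS, which Section 10 allows, does not resolve this. The AE blind binds every examining rater, including one who scores only the CGI.
- The word independent in 9.4.5.5 does not mark out a special CGI rater. Sections 9.4.5.1 to 9.4.5.3 use it for the MoCA, SDMT and TMT, which Section 10 lists beside the MDS-UPDRS.

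So no reading satisfies both.

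**2. When does this reach the primary endpoint?** Three conditions must all hold:
- The CGI scorer obtains AE information, contrary to Section 10.
- The same person scores the MDS-UPDRS. Section 10 makes the rater responsible for all efficacy assessments, but also says one rater need not do them all and requires at least two per site. This is permitted, not required.
- The knowledge precedes the Part III rating. The Visit 9 order provides for this.

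**3. Is the Visit 9 order intended?**
- Section 9 names the patient-completed instruments to be done before clinical contact: BDI-II, PGIC, PDQ-39, EQ-5D and HRPQ. It puts the CGI in the other group, given by blinded staff.
- Part 1 (Sections 10.1.1.2 and 10.1.1.8) places the CGI after the MDS-UPDRS and PD-CRS.
- Part 2 (Sections 10.1.2.2 and 10.1.2.9) places it before them.

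The Part 2 placement conflicts with both.

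**4. Size.** The protocol gives no rate at which raters learn of AEs, no difference between arms in that rate, and no effect of such knowledge on Part III. The bias therefore cannot be computed. What can be shown is how sensitive the primary test is to an assumed net bias b between arms.
- Plan's own figure (Section 11.1): difference 4.06, SD 10.01, two-sided 0.05, 80% power, 10% loss. The normal approximation gives 2 × (1.960 + 0.842)² × (10.01/4.06)² = 95.4, so 96 per arm. The t-test needs 97, and 97/0.9 = 107.8, so 108. The stated 108 is reproduced and is not in dispute.
- SE with 97 per arm: 10.01 × √(2/97) = 1.44.
- Type I error: 1 − Φ(1.96 − b/SE) + Φ(−1.96 − b/SE).
- Power if b runs against the drug: Φ((4.06 − b)/SE − 1.96).

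| Assumed b (points) | b/SE | Type I error | Power if bias runs against drug |
|---|---|---|---|
| 0 | 0 | 5% | 81% |
| 0.5 | 0.35 | 6.4% | 70% |
| 1.0 | 0.70 | 10.7% | 57% |
| 2.0 | 1.39 | 28.5% | 30% |

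The values of b are assumptions chosen to span a range. Nothing in the protocol says that any of them is likely.

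**The case against.** The strongest reply is that a compliant rater never learns of AEs. Section 10 forbids it, Section 9.4.5.5 does not tell the rater to ask about AEs, and the Visit 9 list puts the AE review after all the scales. On that reading one exploratory subscore is poorly defined and the primary endpoint is untouched. This stands as a limit on the consequence. It does not remove the contradiction, because the item is then scored without the information that defines it.

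Other replies also have force:
- The first block at Visit 9 is headed as something to do whenever possible before contact with the Investigator. That qualifies timing relative to the Investigator. It does not move the CGI behind the MDS-UPDRS.
- The same order on Day 1 is harmless for AEs, since it precedes the first dose. Weeks 13, 26 and 39 have no CGI.
- Part II is self-administered, so only Part III is open to a rater's influence.
- The CGI form in Appendix M is not shown, so how the form handles the item cannot be checked. The text of 9.4.5.5 stands regardless.

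A reader might infer that the AE blinding protecting the primary endpoint is lost at Week 52. The documents do not support that. It would need one person to score both scales and to obtain AE information against an explicit prohibition. AE knowledge would in any case be a possible cue and not the treatment code.

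**Conclusion.** The contradiction between Section 9.4.5.5 and Section 10 is real and depends on no assumption. Its certain consequence is limited: the exploratory treatment-response item cannot be scored as defined by the person assigned to it. Its conditional consequence is that AE knowledge can influence Part III at Week 52. That requires the rater to obtain AE information and also to score the MDS-UPDRS, and the Visit 9 order makes it easier. The order is a secondary issue: a rater who learned of AEs at Week 52 would remain informed for later ratings in the long-term follow-up, whatever the sequence.

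The size of any bias is unknown. The table above shows the sensitivity of the test to assumed biases and is not an estimate. The passages should be reconciled. The stated sample size is unaffected.

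**What to change.** 1. In Sections 9.4.5.5 and 10, limit the blinded rater to CGI severity and CGI change. Drop the treatment-response item, or have the treating neurologist, who already assesses AEs, score it.
2. In Section 10.1.2.9, and in 10.1.2.2 for consistency, place the CGI after the MDS-UPDRS and PD-CRS, as Part 1 does.
3. Where Week 52 ratings are already done, document who scored the treatment-response item, whether AE information was used, and whether that person also scored the MDS-UPDRS.

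The cost is wording in a few sections and one rater instruction, with no new visits or staff. The downside is that the exploratory treatment-response item is lost, or is scored by a clinician who knows the AEs.
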